3.1 General Design

TMS will be administered to either the fMRI-guided target or DLPFC in a randomized, single-blind design. 40 patients diagnosed with Post-Traumatic Stress Disorder (PTSD) or trauma induced Major Depressive Disorder (MDD) and symptoms of depression, as determined by meeting the DSM criteria for PTSD or MDD as a primary diagnosis and scoring ≥10 on the PHQ-9, will be recruited for this study. They will be otherwise healthy adults, aged 18-60, with PTSD or trauma induced MDD as primary diagnosis and without current diagnoses of significant, problematic substance use disorders or with present or past diagnoses of psychosis or bipolar illness. All subjects will receive active TMS, so there is no placebo or sham condition. However, the patients will be blinded as to whether their site of stimulation is based on the clinical standardized targeting method or our novel fMRI-guided targeting method. TMS is administered to one of these two sites over a two-week period, and then TMS will be administered to the other site over a subsequent two-week period following a three week wash out period. All subjects will receive TMS to both sites as a part of the study, but the order is randomized and counterbalanced. All participants will be recruited through the community via study advertisements and through the University of Pennsylvania and the VA. Subjects can express interest by contacting the study staff; in most cases, this will serve as the primary method for acquiring contact information. Physician referrals and the use of the Penn Data Analytics Center will also be incorporated as recruitment methods. Section 4.3 further elucidates all recruitment methods. Prior to any study visits, all subjects will be screened in a telephone interview with a trained member of the study staff or via a self-report screening survey. The first study session will consist of a consenting and extended screening visit. The information collected in this initial visit will determine if the subject meets all inclusion criteria. We will also demonstrate TMS to ensure the subject is comfortable with all study procedures. At the second study session, participants will undergo an MRI procedure for 60 minutes. This will be used to generate the TMS targets for the study. Subjects will then return every weekday (5 days per week, minimum of 4 days per week) over two weeks to receive the TMS treatment (10 sessions). These visits will last approximately 60 minutes each. The daily administration of TMS is a necessary component of the study, as it is consistent with the standard operating procedure for FDAapproved clinical TMS. During the 2 weeks of TMS treatment, subjects will undergo the many of the same clinical assessments used during the screening and baseline visits, in order to examine changes in symptoms. Subjects will then spend 3 weeks away from the study team; during the break, there will be two phone/survey visits used as a safety assessment. After this break, subjects will then return every weekday (5 days per week, minimum of 4 days per week) over two weeks to receive the TMS treatment (10 sessions) to the other site examined in the study. Upon completion of the study, scheduled phone and survey visits will take place every 4 weeks (+/-7 days) over the subsequent 6-month period to monitor continued stability of clinical improvement and/or remaining clinical symptoms. Overall, this study consists of 1 consent/screening visit, 1 MRI scan, 20 total visits for TMS treatment, and 8 phone visits.

3.1.1 Screening Phase

Potential participants will be recruited from the community or they may be approached by collaborating clinicians (see recruitment plans) to explore participant's interest in taking part in a research study. Those who are interested will either complete a phone screen or self-report screening form via RedCap. Those who pass the screen will receive an appointment to come to the research location to review the informed consent form and conduct the baseline diagnostic assessment screen to determine eligibility. Informed consent will be obtained upon arrival at this initial visit and before any study-related procedures are conducted. All subjects will have the opportunity to ask questions before signing a consent form. The rest CONFIDENTIAL

of this initial visit will be an extended screening, which includes a structured diagnostic interview, psychiatric and medical evaluation, and collection of demographic information. Subjects will undergo a short demonstration of TMS to ensure that they are comfortable with all study procedures. This process involves adjusting the TMS device to a moderate level of stimulation and administering single pulses to the prospective TMS sites. A structured interview, *Diagnostic and Statistical Manual of Mental Disorders - DSM-5* will be used to assess the DSM criteria for PTSD or trauma induced MDD and the PHQ-9 will be used to assess presence of depressive symptoms. During the COVID-19 pandemic, the screening visit will be conducted virtually to limit in-person visits. The consent process will take place with a coordinator virtually and then documented via Recap (as discussed with the IRB in 2020). TMS would be tested at the second visit instead of at the screening visit.

3.1.2 Study Intervention Phase

Allocation to Interventional Group - Subjects will be randomly assigned to receive TMS at either the fMRIguided target or the DLPFC during this study. This is a single-blind study, so the researchers will know the site of administration for each subject, whereas subjects will remain blinded. The research team will be responsible for randomizing subjects using a computer-based randomization algorithm.

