4.3 Subject Recruitment

All participants will be recruited through the University of Pennsylvania, the Veterans Administration Medical Center, and surrounding community to find 80 patients with PTSD and trauma induced MDD and depressive symptoms. All subjects will express interest by initiating contact with the research staff or by confirming with their referring physician that they wish to be contacted for a screening procedure. All subjects fitting inclusion criteria will be approached by study staff to continue in the study. Additional recruitment methods will include Penn media services, social media, online advertisements (e.g. Craigslist), and fliers to be posted in the local community.

This study will also utilize Facebook as a recruitment resource. The CNDS Lab account will list posts on its page twice a week advertising for this specific study. This account is managed by [name].

In order to facilitate the enrollment of interested subjects in multiple studies, center-wide general prescreening forms phone screen and self-report screen will be used. Because the Center for Neuromodulation in Depression and Stress has numerous studies that are all closely related, in both purpose and eligibility criteria, a general pre-screening (both phone and self-report) has been created. Many participants will be eligible for multiple studies and will be presented the opportunity to participate in all studies that they are eligible for. An additional benefit of a shared or general pre-screening is that participants who do not qualify for a specific study can be informed of other studies they are eligible for. It will be clearly explained to all individuals that this pre-screening is for multiple studies and that their information will be stored in REDCap.

Since approval of v1.0, the center-wide prescreening has successfully increased enrollment of eligible participants across studies as well as significantly reduced burden on interested participants and study staff. The proposed modification (Sept. 2019) to the screening form (v3.4) will update eligibility criteria to be more reflective of current protocols and reduce participant response burden by optimizing branching logic, clarifying language, and implementing standard symptom severity scales. This modification (v3.4) will not be available to potential participants until all actively enrolling CNDS studies obtain IRB approval. Until

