5.4 Blinding

The administering clinician will be blinded as a part of this study. All subjects will receive TMS to both stimulation sites (fMRI-guided target/ DLPFC) as a part of this study in 2-week intervals. The order of site of stimulation is randomized and counterbalanced.

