5.5 Administration and Accountability

Staff will be trained on the protocol and inclusion/exclusion criteria. TMS protocols will be administered by specially-trained staff in the CNDS. All TMS staff will be trained by the PI ([name].) and the Center Director ([name].). These procedures are in accordance with the "Safety, ethical considerations, and application guidelines for the use of transcranial magnetic stimulation in clinical practice and research" (Rossi et al., 2009). MRI scans will be conducted by MRI technologists trained at the Center for Advanced Magnetic Resonance Imaging and Spectroscopy (CAMRIS).

6 Study Procedures

Procedure Visit Number	Screening (2-3 Hours)	Baseline (2- 3 Hours)	TMS Treatment (1 ½ hours)	*3 week break* 2 Phone calls (30-60 minutes) N/A	TMS Treatment (1 ¹ / ₂ hours)	Follow-Up Calls (30-60 minutes) N/A
Visit Type	In-person (Virtually during COVID-19)	In-person	In-person	Phone	In-person	Phone/ Surveys
Study Duration	2-3h	2-3h	1-2h	30min	1-2h	30min
Informed Consent	Х					
Clinical Assessments	Х	Х	X	Х	X	Х
Neurocognitive Assessments		Х	X (Visit 11 Only)		X (Visit 22 Only)	
MRI		Х				
TMS	X (Demonstration Only)		X		X	
Behavioral Tasks			Х		Х	
EEG and eyetracking		Х	X (Visit 11 Only)		X (Visit 22 Only)	

***Visit 11 and Visit 22 may take up to 2 hours to complete

During the COVID-19 pandemic the screening visit and other procedures may be completeled remotely.

Does your study use MRI? (CAMRIS is the appropriate contact for all studies involving MRIs) \boxtimes Yes \square No

Check of all that apply: □ 1.5T MRI

	1.51	MR
\boxtimes	3T N	1RI
	7TM	RI

Does the MRI use investigational sequences and/or coils? (See Experimental Device Clause)

🗌 No

⊠ Yes

Unsure (if unsure you need to contact CAMRIS)

Does your study include pregnant women? (See Pregnancy Clause and Justification)

Yes

Does the MRI require the use of Contrast Agents? (See Contrast Risks)

CONFIDENTIAL

This material is the property of the University of Pennsylvania.

🛛 No

	□ Yes	No	
Does your stud	y involve the exposure to	radiation, radiotracers and/or radiological imaging modalities?	
	Yes	\boxtimes No (If No, no RRSC review is needed)	
Will any of the i of a subject's pa	radiation exposure result articipation in the researc Yes	from procedures that are or could be performed solely as a result the protocol? \fbox No	
Ultrasound	□ Yes	⊠ No	

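### The unblinded research team runs the randomisation with no described concealment and may suspend it by hand; this exposes the 6-month comparison directly and the within-patient site contrast under specific conditions

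*Combined protocol and SAP*

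**What the plan says.** All references are to the combined protocol and SAP.

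- **Who randomises.** Section 3.1.2: "The research team will be responsible for randomizing subjects using a computer-based randomization algorithm".
- **Who knows the site.** Section 3.1.2: "This is a single-blind study, so the researchers will know the site of administration for each subject, whereas subjects will remain blinded".
- **Clinician blinding.** Section 5.4: "The administering clinician will be blinded as a part of this study". This conflicts with section 3.1.2.
- **What is randomised.** Section 3.1: "All subjects will receive TMS to both sites as a part of the study, but the order is randomized and counterbalanced". The two rounds are separated by a three-week washout.
- **Who recruits and who treats.** Section 4.3: "All subjects fitting inclusion criteria will be approached by study staff to continue in the study". Section 5.5: "TMS protocols will be administered by specially-trained staff in the CNDS". Neither section says whether these people are the same as, or separate from, those who randomise.
- **Suspension of randomisation.** Under section 7.4.1, once 10 participants have been randomised to each order, the two groups are compared on age, education, gender and symptom severity. If they differ systematically, randomisation is paused and patients are placed in one order or the other to restore balance.
- **Analysis.** Section 7.4 plans a Site x Time ANOVA from pre-treatment to the end of each round, and a second one from pre-treatment to 6 months. No period, sequence or carryover term is named.

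No section describes an independent list holder, a concealed sequence, or release of the allocation only after eligibility and baseline are complete.

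**The concern.** Concealment protects a trial from having allocation influenced, knowingly or not, by what staff think of the next patient. Here the group that randomises also knows the sites already given, and the order is counterbalanced, so later allocations may be open to inference. The Study Summary and section 2 state the hypothesis that the fMRI-guided target is better. Section 7.4.1 goes further than silence on concealment: it plans for the team to assign patients by hand, with symptom severity among the criteria.

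The crossover removes much of the usual harm, but not all of it. A patient characteristic matters to the site contrast if it alters how much more the patient improves in round 1 than in round 2. The plan gives three plausible routes:

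- Entry requires a PHQ-9 of 10 or more, so regression to the mean would fall mainly in round 1.
- Strong early responders may have little room left to improve in round 2 (a floor effect).
- Benefit from round 1 may carry past the three-week washout.

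At stake is the primary question, the difference between the two sites, and the secondary look at whether any difference persists to 6 months.

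**Working it through.** **The plan's own figure.** The plan gives no figure for allocation bias. Its one calculated figure, at least 6 patients (section 7.3), reproduces by the two-sided normal approximation: ((1.960 + 0.842) / 1.225)² = 5.23, rounded up to 6. It concerns symptom change, not the site contrast, and is not used below.

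**Step 1: when prognosis cancels.** Let D be a patient's round-1 minus round-2 improvement. With a period term, the site contrast is half the difference in mean D between the two orders. Anything that shifts both rounds equally drops out of D. A simulation with 40 patients, no true site effect, strong selection of order by prognosis and a period effect of up to 1 SD gave bias of 0.00 and a false-positive rate of 4.6-5.3% when prognosis left D unchanged.

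**Step 2: when it does not cancel.** Suppose half of the patients have a D larger by G than the other half. A share q of that half gets the guided site first, and a share 1 - q of the other half does. Then

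bias = (2q - 1) x G / 2.

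All inputs except the 40 completers are assumptions: 20 per order, G = 6 points on the depression scale, SD of the random within-patient difference 7.

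- q = 0.65: 0.30 x 6 / 2 = 0.9 points
- q = 0.75: 0.50 x 6 / 2 = 1.5 points

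Simulated false-positive rates are about 9-10% and 21-22%, against about 3% at q = 0.50. (The 50% figure is below 5% because the two halves are then exactly balanced between orders while still adding to the pooled variance.)

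**Step 3: imperfect prediction.** Early response is not known at allocation; staff could act only on a predictor. If the half they pick correlates r with the true half, the bias is multiplied by r.

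| r | q = 0.65: bias, false positives | q = 0.75: bias, false positives |
|---|---|---|
| 1 (upper limit) | 0.9, about 10% | 1.5, about 21% |
| 0.5 | 0.45, about 6% | 0.75, about 9% |
| 0.3 | 0.27, about 5% | 0.45, about 7% |

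Halving G to 3 points halves every bias.

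**Step 4: can it be adjusted away?** A period term does not remove this bias. If the steering variable is recorded at baseline, including it as a covariate does: in the same simulation the residual bias was about zero and the false-positive rate about 5%. Steering on unrecorded information cannot be corrected.

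**Step 5: the 6-month comparison.** By 6 months every patient has had both sites, so a site factor can only distinguish the orders. That is a between-patient comparison. If the favoured half differs by G in 6-month improvement, the bias is (2q - 1) x G x r, with no halving and no cancellation: 0.30 x G to 0.50 x G at r = 1. Prognosis of any kind enters here, not only prognosis that changes D.

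**Step 6: concealment restored.** With order independent of prognosis, simulated bias is about 0 and the false-positive rate 4.8-5.3% for every period effect and interaction tried.

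**The case against.** The strongest reply is that each patient is their own control, a computer algorithm assigns the order, and the administering clinician is blinded. Much of this stands.

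- Prognosis common to both rounds does cancel (Step 1). A lower starting severity in round 2 shared by all patients is a period effect, and cancels between balanced orders.
- The algorithm is not itself a route for bias. A reader might infer that staff choose the order or can predict it. The documents do not say so: block sizes and list visibility are not disclosed. Section 7.4.1 is the one place where assignment by staff is actually planned.
- A reader might infer that the same individuals recruit, randomise, treat and know the site. The documents do not state this. They are silent on separation of roles, and section 5.4 contradicts section 3.1.2 for the treating clinician. Blinding that clinician would not, however, conceal the sequence from those who randomise.
- A reader might infer that the site contrast will be biased. That needs both steering and an interaction between the steering characteristic and round. The plan calls the gap a washout and only explores whether benefit is maintained, so the interaction is plausible but not established.
- Rebalancing on severity under section 7.4.1 uses a recorded variable, so adjustment for it is possible. The named ANOVA does not include it.

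What survives is that concealment is not described, the override is written into the plan, and the 6-month analysis has no crossover protection.

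**Conclusion.** The point holds in a limited form. The plan leaves allocation with an unblinded team, describes no concealment, and permits randomisation to be suspended in favour of assignment by baseline characteristics. The 6-month Site x Time comparison is directly exposed. The primary within-patient contrast is biased only if order follows something that changes the round-1 minus round-2 difference.

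The size is illustrative. The perfect-prediction figures in Step 2 are a ceiling; with a modest predictor the bias is about 0.3-0.8 points and false positives are 5-9%. The gap of 6, the SD of 7, the steering shares and the correlations have no source in the documents. Nothing in the documents shows that steering has occurred or is intended. This should be corrected because the remedy is cheap and can be written down in advance; it is not grounds to conclude that the trial's contrast is invalid.

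**What to change.** 1. **Section 3.1.2.** State that the order list, in permuted blocks of varying size, is generated once before enrolment by an existing colleague who does not enrol, treat or rate patients. Load it into REDCap, which the study already uses, and release each allocation only after eligibility and the baseline scales are locked.
2. **Section 7.4.1.** Delete the rule that suspends randomisation; left in place, it would defeat the concealed list. If balance on severity is wanted, stratify the list by baseline severity.
3. **Sections 3.1.2 and 5.4.** Reconcile the two statements on blinding, and say which roles know the site.

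The cost is a short amendment to these sections and a REDCap set-up, with no extra visits or staff. The small downside is that staff learn the order only after baseline is complete and can no longer rebalance by hand. The sample size does not change.

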3.2 Study Endpoints

3.2.1 Primary Study Endpoints

The primary endpoint will be clinical improvement due to TMS at either of the two target regions. The study will focus on a target region of the fMRI-guided target and the standard DLPFC target, which is an FDA-approved rTMS treatment site. TMS-induced changes in brain activity are likely different for these two stimulation sites, despite their proximity. The aim of this study is to establish if using targets defined by resting connectivity in patients can be more effective at treating MDD/PTSD compared with standard targets.

3.2.2 Secondary Study Endpoints

The secondary endpoint to be analyzed in this study will be the relationship between baseline fMRI activity and the clinical improvement over the course of the study in the MDD/PTSD patients.

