2.2 Secondary Objectives (if applicable)

• To assess the correlation between resting-state connectivity prior to TMS and the degree of clinical change in response to TMS treatment targeting this circuit.

3 Investigational Plan

Visit #0:	Consenting / Screening procedures	
Visit #1/Baseline:	Baseline MRI Scan to determine TMS targets, clinical assessments, and	
	neuropsychological assessments	
Visit #2-11:	Targeting + TBS treatment and clinical assessments	
Break:	Subjects spend 3 weeks away from the lab,	
(Phone/Survey) Visits #	12 and 13: Clinical assessments	
Visit #14-23:	Targeting + TBS treatment and clinical assessments	
(Phone/Survey) Visit #2	4-29: Clinical assessments	
See Section 6. Study Procedures for specific assessments at each visit		

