6.7 Safety Evaluations

Only individuals trained by the Principle Investigator ([name].) and Center Director ([name].) will dispense TMS. The licensed physician ([name] or a suitable medically trained stand-in) will closely supervise any medical instability in patients and will specifically be responsible for training and overseeing syncope and seizure management which are not expected given our screening process but are the two primary health risks with TMS treatment.

[name], a board certified physician, will review all questionable screens for MRI and TMS safety and will be physically present (or a reasonable medically trained stand-in) for every TMS session conducted on any participant who indicates greater than minimal risk for experiencing syncope or a seizure in response to TMS.

Only research personnel will have keys and access to the TMS devices.

7 Statistical Plan

All recruitment will be conducted through the University of Pennsylvania, the Veterans Administration Medical Center, and surrounding community to find 80 patients with PTSD or trauma induced MDD and depressive symptoms. It is anticipated that a large portion of individuals will screen fail, withdrawal from participation or have unusable data. Therefore, 80 individuals will be consented/enrolled in this study, to ensure that there are 40 patients who complete the full protocol with usable data. This sample should provide us with adequate data to compare treatment sites relative to one another, since all patients will receive the standard targeting for TMS and also fMRI-guided TMS.

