7.2 Secondary Endpoints

The secondary endpoint of this study will be the correlation between resting-state connectivity prior to TMS and the degree of clinical change in response to TMS treatment targeting each circuit.

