7.4.2 Efficacy Analysis

Efficacy analyses will focus on comparisons between clinical symptoms at baseline, after the first 2-week treatment period, and at the end of the second 2-week treatment period. As noted above, the primary endpoint of this study will be a comparison focusing on clinical improvement due to TMS performed at either the standard brain target or the fMRI-guided brain target.

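### Section 3.2.2 relates the baseline scan to improvement over the whole crossover, while 2.2 and 7.2 relate it to the response to stimulating a given circuit; one per-site definition is needed.

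*Combined protocol and SAP*

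**What the plan says.** The secondary endpoint is described in three places in the combined protocol and SAP.

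- Section 3.2.2 (Secondary Study Endpoints): the "relationship between baseline fMRI activity and the clinical improvement over the course of the study in the MDD/PTSD patients". No site or treatment round is named.
- Section 7.2 (Secondary Endpoints): the "correlation between resting-state connectivity prior to TMS" and "the degree of clinical change in response to TMS treatment targeting each circuit".
- Section 2.2 (Secondary Objectives): the same predictor as 7.2, but "the degree of clinical change in response to TMS treatment targeting this circuit", so one circuit rather than both.

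The design is a two-period crossover. Section 3.1 states: "All subjects will receive TMS to both sites as a part of the study, but the order is randomized and counterbalanced". It also states that "TMS will be administered to the other site over a subsequent two-week period following a three week wash out period".

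Section 7.4.2 lists the efficacy comparisons as "clinical symptoms at baseline, after the first 2-week treatment period, and at the end of the second 2-week treatment period". Neither it nor the rest of 7.4 describes an analysis of the secondary endpoint.

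**The concern.** The descriptions differ in both halves of the correlation. The predictor is fMRI activity in 3.2.2 and resting-state connectivity in 2.2 and 7.2. The outcome is improvement across the study in 3.2.2 and response to stimulating a circuit in the other two.

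The outcome difference matters more because of the crossover. By the end of round 2 a completer has had ten sessions at each of two targets, so a single whole-study improvement contains the response to both. Objective 2.2 asks whether connectivity of a circuit predicts the response to treating that circuit, and such an outcome cannot answer it. A positive result could reflect either site, both sites, or general prognosis.

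This is the plan's only stated secondary endpoint. With 7.4 silent, an analyst could follow either definition and claim to be within the protocol, including after seeing both results.

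**Working it through.** The plan gives no sample size, power or expected correlation for this endpoint, so there is no figure of its own to reproduce. The check has two parts: what a whole-study correlation can identify, and what it does to power.

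**Inputs**

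- n = 40. The opening paragraph of section 7 (Statistical Plan) plans enrolment "to ensure that there are 40 patients who complete the full protocol with usable data".
- Two-sided alpha 0.05 (assumed for this endpoint).
- r_a, the correlation of the scan measure with change at the site of interest: 0.50 (assumed).
- r_b, its correlation with change at the other site: 0, 0.25 or 0.50 (assumed range).
- ρ, the correlation between the two rounds' changes: 0 or 0.5 (assumed range).
- Equal variance of change in both rounds, with whole-study improvement taken as the sum of the two changes, ignoring drift over the break (assumed).

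**Formulas**

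Whole-study correlation: r_total = (r_a + r_b) / √(2 + 2ρ).

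Power by Fisher's z: Φ(atanh(r) × √(n − 3) − 1.96), with √37 = 6.083.

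**Attribution**

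The numerator holds only the sum r_a + r_b. With ρ = 0, the pair (0.50, 0) gives 0.50/1.414 = 0.354, and the pair (0.25, 0.25) also gives 0.354. A predictor specific to one circuit and a weaker one common to both give the same whole-study correlation. This does not depend on the size of the effect.

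**Power**

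Per-site outcome: atanh(0.50) = 0.549; 0.549 × 6.083 − 1.96 = 1.38; power 0.92.

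Whole-study outcome:

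| r_b | r_total, ρ = 0 | Power | r_total, ρ = 0.5 | Power |
|---|---|---|---|---|
| 0 | 0.50/1.414 = 0.354 | 0.61 | 0.50/1.732 = 0.289 | 0.44 |
| 0.25 | 0.75/1.414 = 0.530 | 0.95 | 0.75/1.732 = 0.433 | 0.81 |
| 0.50 | 1.00/1.414 = 0.707 | above 0.99 | 1.00/1.732 = 0.577 | 0.98 |

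If r_a is 0.30 instead, per-site power is 0.47. With r_b = 0, whole-study power is then 0.26 (ρ = 0) or 0.19 (ρ = 0.5).

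So the whole-study outcome loses power when the scan measure is specific to one site. It can match or exceed the per-site outcome when the measure predicts response at both.

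**The case against.** The strongest reply is that 3.2.2 is loose shorthand. It never says that the sites are summed or that one end-of-study change score will be used, and its wording can be read as a time frame. The preceding section, 3.2.1, frames improvement by target region. Sections 2.2 and 7.2 are both treatment-specific, and 7.2 belongs to the statistical plan. This stands in part: the pooling follows from 3.2.2 read with the crossover in 3.1 and is not stated. It does not remove the conflict, because no section ranks one definition above the other.

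A reader might also infer that following 3.2.2 necessarily costs power because the other site's improvement is noise. The documents do not support that. The Study Summary calls the targets two sub-regions of the DLPFC, 3.2.1 notes how close they are, and the opening of section 2 hypothesises that connectivity predicts symptom reduction after TMS without naming a site. Zero correlation with the other site's change is one possible case, and it alone produces the large losses. For the site-neutral hypothesis in section 2, a whole-study outcome is a legitimate measure.

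The per-site outcome is not automatically clean either. Round-2 change needs a starting score, and the response to round 1 may carry over into round 2.

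**Conclusion.** The inconsistency is real and should be resolved before analysis. Sections 3.2.2 and 7.2 define non-equivalent endpoints, nothing in 7.4 chooses between them, and the whole-study version cannot answer objective 2.2 because it cannot attribute a correlation to a circuit. Those conclusions rest on the text and the design alone.

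The size of any power effect is illustrative. It rests on the assumed 0.50 and on an unknown relation to the other site's change, and it runs from a fall to 0.44 to a gain above the per-site 0.92. It should not be cited as a demonstrated loss. The point concerns a secondary correlational endpoint and does not touch the primary Site x Time comparison in 7.4.

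**What to change.** Replace the sentence in 3.2.2 with the 7.2 definition and add the analysis to 7.4, stating that:

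- the predictor is resting-state connectivity before TMS, in place of fMRI activity;
- the outcome, for each site, is symptom change on a named scale over the round delivered at that site;
- round-2 change starts from the last score before round 2, not from the study baseline;
- the analysis adjusts for round order.

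Align 2.2 (*this* circuit) with 7.2 (*each* circuit), so that the number of correlations is fixed. Whole-study improvement may stay as a labelled exploratory analysis of the site-neutral hypothesis in section 2.

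Two sources for the round-2 starting score are already scheduled. Section 6.6 places the efficacy scales in the break, with contacts about one and two weeks after Visit 11 (6.2.3). Section 6.2.2 has a short clinical assessment before each session, but does not list its scales. The plan should say which source is used. If the pre-session assessment lacks the chosen scale, the second break contact serves, roughly a week before round 2.

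The cost is a few sentences, with no new scan or visit. The downsides are two correlations instead of one and possible carryover into round 2, which should be acknowledged when the results are interpreted.
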